#### Repeated measures analyses (including observed outcome data only at 1, 3 and 12 months)

Similarly to the analyses of 12-month data, we will await results of the sensitivity analyses at 3month follow-up prior to making any decisions regarding sensitivity analyses of the repeated measures analyses including data from 1-, 3- and 12-month follow-up.

Again, the primary analysis will use the intention to treat principle : all recruited participants will be analysed according to their randomised group. This is the originally intended primary analysis and adds the participants recruited to replenish the sample following the disruption due to app outage to the original intended sample.

Options for sensitivity analyses for repeated measures analyses include the following.

1. Exclusion of participants whose intervention was disrupted prior to 12-month follow-up (Groups 1, 2 and 3).

2. Exclusion of participants whose intervention was disrupted prior to 3-month follow-up (Groups 2 and 3; moderate/severe disruption).

#### **CACE** analyses

CACE analyses will include only data from those participants who did not experience disruption prior to 3-month follow-up, as it will be impossible to distinguish between participants who chose not to adhere to the intervention and those that were unable to adhere due to the app outage; this inability to distinguish between causes of non-adherence could lead to bias in the analysis.

#### **Missing data**

The primary analysis (including all randomised participants according to their allocation using observed data only) will be repeated using observed and imputed data for the full sample (i.e. the original sample and replenished sample). See Section 6.5 above for further details on methods to address missing data.

#### 6.10 Adverse events

The main anticipated adverse event in this trial is deliberate self-harm. Serious adverse events will be reported descriptively by treatment arm, also the number of participants in each treatment arm who have experienced at least one serious adverse event will be reported. Inferential analyses will also be performed using the count of events (Poisson or negative binomial model) and the number of participants experiencing the outcome at least once during the 12-month follow-up period (logistic regression), using observed data on an ITT principle with adjustment for covariates as for the outcome data analyses (Table A.14).

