As with all psychological interventions, individuals reflect on their difficulties, which can produce temporary increases in distress, but no more than would commonly occur in daily life. Prior work has provided positive feedback on the rumination self-help intervention and indicated reductions in poor mental health over 12 months, with no serious adverse events reported: as such, this component of the trial may benefit individual participants. The likeliest outcome for users who do not find the intervention of benefit is their disengagement from it. In addition, all participants receive more intensive monitoring, with processes to identify and direct all relevant participants to potential sources of help (e.g., youthinmind.info; Samaritans; General Practitioners; Teléfono de la Esperanza; Telefonseelsorge; websites providing contact details of psychotherapists and psychiatrists, as relevant; websites proving clinically approved advice for mental health conditions).

As part of our policy for addressing risk and prioritizing the welfare of participants, participants are provided with links to online support, access to contact the trial team, and automatic signposting to help and guidance if reporting risk (e.g., suicidal thoughts, as indexed in items within outcome measures such as the Patient Health Questionnaire-9, PHQ-9 on the screening or follow-up websites) or levels of symptoms suggesting a need for help within any of the assessments within the cohort study. These messages include general information on the presenting symptom, recommended actions to make themselves safe, and advice to seek medical help, and direct links to relevant national sources of help.

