9.3 Recording and reporting of SAEs, SARs AND SUSARs

All serious adverse events that are trial or treatment related will be recorded and immediately reported to the Chief Investigator and within 2 working days to the trial sponsor. If these are also classed as unexpected they will be reported to the relevant ethics committees. We will, in line with other complex intervention studies, monitor non-serious adverse events, serious adverse events that are not trial or treatment related, serious deterioration, and active withdrawals from treatment, with specific questions in the follow-up and in response to specific participant-initiated reports. Symptoms of depression or anxiety will not be defined as adverse events unless suicidal ideation, plans or an attempt has been made. The reporting period for all events and reactions will be from referral to 12month post baseline follow-up. Data on any adverse events will be collected by a member of the research team at each assessment.

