16.5 Safety Reporting Flow Chart

Safety Flow Chart Version 1

AE reported on screener follow up. CTU website logs all AE and reported reasons

Website sends alert to site PI, site researcher and trial manager if AE reported and ppt ticks that its related to trial participation AE reported to site Researcher via email or phone, Risk log to be completed and submitted to site PI within 2 days.

AE Monitoring

All sites to produce end of monthly report of AE/SAE, unblindings and protocol violations to trial manager

Site researcher attempts to contact ppt within 2 days to find out more if insufficient data to complete risk log

Trial manager to review site reports and CTU websites log of AE/SAE at the end of every month and provide monthly report for CI and DMEC representative /

If SAE reported to site Researcher via email or phone or website alert Risk log to be completed (contacting ppt if necessary) and submitted to site PI, trial manager and CI within 2 working days.

> If SAE reported to CI TM/CI informs the sponsor, steering committee and DMEC within 2 working days of event being reported

If serious concerns for patient wellbeing/scientific rigor then discussion with ethics committee within 7 days of event being reported

SAE check-AE questions to be asked at follow up, or if reported to the site researcher by phone/email: Have you experienced any health emergencies, accidents, unplanned hospital admissions in the last 3 months? What happened? (please describe) What caused this? Please tick all that apply Sports injury Traffic accident Assault Self injury Taking part in the trial Physical illness Work Other please state

AE check-Overall, has taking part in the trial so far made you feel much worse.....no effect.....much better? Please give details Have you had any problems with the App. If yes please give details:

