## 6.2 Purpose of the analyses

The purposes of the statistical analyses are as follows:

- 1. to provide descriptive baseline data by trial arm;
- 2. to report attrition at all follow-up timepoints;
- 3. to report individual outcome missingness at all follow-up timepoints;
- 4. to report adherence to the intervention in the active treatment arms;
- 5. to evaluate effectiveness of the active interventions relative to control, and the personalised active intervention relative to the standard active intervention, using inferential analyses;
- 6. to perform additional analyses to investigate potential moderators of the intervention effect; and
- 7. to provide descriptive data on serious adverse events.

Details of the quantitative mediation analyses will be described in a separate mediation analysis plan.

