|  |   |  |                  |
|  |   |  |                  |
|  |   |  |                  |

Table A.14 Adverse events during 12-month follow-up

|  | Descriptive statist
n/N (%)                             | tics: mean (SD), n; med                                    | ian [min, max] or   | Inferential statist                                      | Global p-value  |  |  |
|--|--|--|---------------------|--|---|--|--|
| Adverse outcome (to
be coded)   | Personalised
digital self-help
+ usual care
(N=X) | Non-personalised
digital self-help
+usual care (N=X) | Usual care
(N=x) | Non-
personalised
digital self-help
+usual care | Personalised
digital self-
help + usual
care | Non-
personalised
digital self-help
+usual care |  |
| Event (count)  |  |  |                     |  |   |  |  |
| Number of
participants
experiencing event at
least once during 12-
month follow-up; n/N
(%) |  |  |                     |  |   |  |  |
|  |  |  |                     |  |   |  |  |
|  |  |  |                     |  |   |  |  |

IRR: incidence rate ratio; OR: odds ratio

Table A.15 Characteristics of people who log on to the website but decline participation

| Characteristic                                       | Personalised digital self-help +
usual care (N=X) |
|--|--|
| Age (years); mean (SD), median                       |  |
| [25 th centile; 75 th centile] |  |
| Age (years)  |  |
| 16–17  |  |
| 18–22  |  |
| Gender   |  |
| Male   |  |
| Female   |  |
| Both   |  |
| Neither  |  |
| Country  |  |
| UK   |  |
| Germany  |  |
| Spain  |  |
| Belgium  |  |
| Ethnic group (tbc)                                   |  |
|  |  |
|  |  |

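### The SAP's by-arm harms analysis is limited to serious adverse events, leaving out the non-serious events, non-serious suicidal ideation and worse-to-better rating that the protocol collects

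*SAP*

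**What the plan says.** SAP section 6.10 states: "Serious adverse events will be reported descriptively by treatment arm, also the number of participants in each treatment arm who have experienced at least one" such event. It continues: "Inferential analyses will also be performed using the count of events (Poisson or negative binomial model"), with a logistic model for participants who have the outcome at least once in 12 months. Item 7 of SAP section 6.2 gives the safety purpose of the analyses as "to provide descriptive data on serious adverse events". The shell that 6.10 cites is headed "Table A.14 Adverse events during 12-month follow-up", and its row label is still to be coded.

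The protocol casts a wider net. Section 8 (Adverse Events) records serious and non-serious events and puts harm questions to all participants, because every arm has an app. Section 9.3 undertakes to "monitor non-serious adverse events, serious adverse events that are not trial or treatment related, serious deterioration, and active withdrawals from treatment". Section 12 bases the evaluation of safety on both classes of event. The flow chart in section 16.5 gives the follow-up item: "AE check-Overall, has taking part in the trial so far made you feel much worse.....no effect.....much better".

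**The concern.** Data on milder harms are collected in all three arms, but the SAP does not commit to showing them by arm. The protocol itself recognises a mild harm that psychological self-help can cause: "individuals reflect on their difficulties, which can produce temporary increases in distress". Such an effect would rarely produce a serious event.

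Suicidal ideation matters more. Protocol section 9.3 excludes symptoms of depression or anxiety from adverse events unless there are suicidal thoughts, plans or an attempt. Ideation can therefore be an adverse event without meeting the seriousness criteria in section 9.1, and it would then fall outside SAP 6.10.

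At stake is the completeness of the harms report. If these data are tabulated only after the results are known, the choice of what to show is open to the charge of selective reporting. SAP section 1.7 treats revisions made after scrutiny of the data and unblinded interpretation as post hoc.

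**Working it through.** No arithmetic applies, because the point rests on no sample size, rate or power figure. The check sets what the protocol collects beside what the SAP says it will analyse.

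| Collected | Protocol source | By-arm analysis in the SAP |
|---|---|---|
| Serious adverse events | Sections 8, 9.1, 9.3 | Yes: 6.2 item 7, 6.10, Table A.14 |
| Non-serious adverse events | Sections 8, 9.3, 12 | None committed to; Table A.14 has room for them |
| Suicidal ideation not meeting the seriousness criteria | Sections 9.1, 9.3; risk questions in Appendix 16.1 | None |
| Worse-to-better rating | Section 16.5 | None: absent from 6.1, 6.3 and every shell |
| Measured worsening on the primary scale | WEMWBS or PHQ-9 at follow-up | Yes: 6.1.1, by the logistic models of 6.3 |
| Symptom, functioning and well-being scores | Section 3.3 | Yes: 6.3, Tables A.4 to A.7 |

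1. **Scope of 6.10.** The count and logistic models follow directly on the sentence about serious events and name no other class. Item 7 of 6.2 independently says serious. Two places agree, so the restriction is not a slip in one sentence.
2. **The table shell.** Table A.14 is headed adverse events and its row is uncoded. It could hold non-serious events, but the text that cites it specifies serious ones. This is an ambiguity to settle and not a commitment.
3. **The rating.** The seven outcomes in SAP 6.1 are WEMWBS, PHQ-9, WSAS, GAD-7, EQ5D-3L, the adapted ADSUS and MINI-IPIP-N. The rating is not among them, and no method or shell refers to it.
4. **Suicidal ideation.** Appendix 16.1 says that follow-up risk answers will be used to monitor suicidality across the arms. That is monitoring during the trial; no SAP analysis corresponds to it. PHQ-9 is analysed as a total score, so its suicidality item is not shown separately.
5. **Oversight.** SAP 3.6 sends all adverse and serious adverse events to the oversight committees. Protocol 7.5 describes aggregate unblinding for serious events only, so the documents do not show that non-serious events would be compared by arm there.

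**The case against.** The strongest reply is that much of what matters is already covered.

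- SAP 6.10 names deliberate self-harm as the main anticipated adverse event, and the report form in Appendix 16.1 lists self-harm as an example of a life-threatening event. The leading expected harm is therefore likely to be within scope.
- Protocol sections 2.1 and 8 describe the extra distress as temporary and no greater than in ordinary life.
- SAP 6.1.1 defines a binary outcome for deterioration of at least the MCID from baseline and analyses it by arm. The symptom scales are compared by arm in both trials.
- Table A.14 is not closed to non-serious events.

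All of this stands, and it rules out two stronger readings. A reader might infer that harm short of a serious event is never compared by arm, or that an app which made a minority worse would look harmless if serious events were rare. SAP 6.1.1, the symptom scores and the monitoring of suicidality contradict both. A reader might also ask for a separate row on active withdrawals. Attrition is already to be reported with confidence intervals and a flow diagram (Protocol 10.3.1), withdrawal time is recorded and a reason requested (SAP 5.4), and non-completers are described by arm (SAP 6.5), so that is largely covered.

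The reply does not reach the remaining gap. Deterioration under 6.1.1 is change on one scale per trial. It is not the participant's own judgement that taking part did harm, and it does not count non-serious events or ideation. For PREVENT its threshold is also unsettled, because the MCID for PHQ-9 is 2.59 in Protocol 10.1.2 and 5.9 in SAP 3.4.

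**Conclusion.** The point holds as a gap in coverage. Non-serious adverse events, suicidal ideation that does not meet the seriousness criteria, and the worse-to-better rating are collected but not compared by arm in the SAP's planned analyses. It is worth correcting because the data already exist and the comparison would improve the safety conclusion. It does not show that the plan would miss a harmful app.

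The documents give no rate for non-serious events or for ratings on the worse side, so no numerical size can be attached. The conclusion rests on two readings: that 6.10 means what it says about serious events, although its table has a broader title, and that ideation need not be serious under section 9.1. That section does allow other important events to be judged serious, so some ideation may reach Table A.14 by that route.

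Two details of the rating are unsettled. Protocol section 8 places brief open harm questions at 3 and 12 months, the schedule in section 16.4 shows adverse event assessment at 1, 3 and 12 months, and section 16.5 says only that the questions are asked at follow-up. The response points between the extremes and the midpoint are not listed.

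**What to change.** - In SAP 6.2 item 7, replace *serious adverse events* with *serious and non-serious adverse events*.
- In SAP 6.10 and Table A.14 add, by arm, n/N (%) of participants with at least one non-serious adverse event, with suicidal ideation on its own row.
- In the same places add the full distribution of the worse-to-better rating at each follow-up at which it is asked. Give n/N (%) on the worse side of the no-effect midpoint, and risk differences with 95% confidence intervals for the three contrasts.
- State the rating's response points and time points. Use those who answered the item as the denominator, since telephone follow-up collects the primary outcome measures only (Protocol 7.7).

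The cost is SAP wording and a few table rows, with no new data collection. The downside is a few more comparisons without multiplicity adjustment, to be presented as safety estimates. The revision should be dated before the 3-month data are examined, so that it does not count as post hoc under SAP 1.7.

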10.3.2 Primary analysis

The primary outcomes (WEMWBS (ECoWeB-PROMOTE); PHQ-9 (ECoWeB-PREVENT) and secondary outcomes will be compared at 3-month follow-up. The primary and secondary continuous outcomes will be reported descriptively (mean and standard deviation (SD)) and inferential comparisons will be reported between the three treatment contrasts ((1) usual practice plus personalised digital self-help EC vs. usual practice alone; (2) usual practice plus non-personalised automated digital CBT self-help vs. usual practice alone; (3) usual practice plus personalised digital self-help EC vs. usual practice alone; (3) usual practice plus personalised digital self-help EC vs. usual practice plus non-personalised automated digital CBT self-help) using linear modelling. All analyses will be based on an intention to treat principle (i.e. according to original allocation irrespective of intervention adherence) and will include participants with complete outcome data at 3-month follow-up, and will adjust for baseline outcome score (where relevant) and minimisation variables (age, gender, country). Furthermore, we will adjust for any baseline participant characteristics that are substantively unbalanced at baseline (defined as a difference ≥ 10 percentage points across categories for a categorical variable, or a difference in means >1 SD for continuous variables), and if the characteristic is thought to be predictive of outcome. Binary secondary outcomes (occurrence of major depressive disorder; generalized anxiety disorder) will be reported as proportions and analysed used logistic regression.

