## 6.3 Analysis methods

All continuous outcomes will be reported descriptively (mean, SD) at all follow-up timepoints. Inferential analyses The primary analyses for the primary and continuous secondary outcomes will use linear regression models with adjustment for baseline score, age (as a continuous variable rather than the dichotomised minimisation variable), country, and any other participant characteristics observed at baseline to be unbalanced across treatment arms (meeting the criteria set out in Section 5.5). The primary follow-up time will be at 3 months; analysis of 12-month follow-up data will also be performed using the same approach. The primary analyses will be based on an intention to treat (ITT) approach (i.e. all participants will be included in the analyses according to their randomised allocation) and will use observed data only.

As a secondary analysis, we will perform repeated measures analyses (using a mixed effects linear regression model with a random effect on participant) for primary and secondary continuous outcomes, including data from participants with observed data for at least one of the three follow-up timepoints. Analyses will be performed to compare both active interventions with usual care, and to compare the personalised active intervention with the standard active intervention. A fixed effect interaction between timepoint and trial arm will be used to evaluate differential treatment effects across timepoints. Adjustments for baseline covariates will be made as for the primary analysis regression models; baseline score will be included as a covariate. Binary outcome measures will be analysed using logistic regression models with adjustments for covariates as above.

The primary analyses will use only the data collected during the time window. The amount of such data will be determined, with the possibility of performing a sensitivity analysis should the amount of data collected outside the time window be substantive. These analyses will be performed using observed data for the ITT population (i.e. according to initial random allocation). No formal adjustments of p-values for multiple testing will be performed; the results for the primary outcome will be interpreted first and the results of the secondary outcomes will then be interpreted in the light of multiple testing. The results of all descriptive and inferential analyses for the primary and secondary continuous outcomes are set out in Tables A.4–A.10.

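### The serious-adverse-event models in SAP 6.10 have no exposure term and no rule for participants seen for only part of the 12 months, so the reported rate and odds ratios may be distorted if dropout differs by arm

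*SAP*

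**What the plan says.** SAP 6.10 first promises descriptive reporting of serious adverse events by arm, then two models. The first: "Inferential analyses will also be performed using the count of events (Poisson or negative binomial model"). The second takes the number of participants "experiencing the outcome at least once during the 12-month follow-up period (logistic regression"). Both are to be fitted "using observed data on an ITT principle with adjustment for covariates as for the outcome data analyses".

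The covariates come from SAP 6.3, which specifies "linear regression models with adjustment for baseline score, age (as a continuous variable rather than the dichotomised minimisation variable), country" and any characteristic found unbalanced at baseline. The footnote to Table A.14 reads "IRR: incidence rate ratio; OR: odds ratio". The table has rows for the event count and for n/N, and none for person-time. Neither document names an offset, a time at risk, a censoring rule or a time-to-event analysis for harms.

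On how events become known:
- Protocol 9.3 has adverse events collected at each assessment, and Protocol 16.4 places these at 1, 3 and 12 months.
- The serious-event item in Protocol 16.5 asks about health emergencies, accidents and "unplanned hospital admissions in the last 3 months".
- The adverse events section of the protocol also uses the hospital and emergency-care items of the AD-SUS. According to SAP 8.8 these look back to baseline at month 3, and to the month-3 interview at month 12.
- Participants can report events by email or telephone at any time.
- Protocol 7.10 stops follow-up for those who withdraw. Protocol 10.1 allows for 40% attrition by 3 months, and Protocol 3.4 expects relatively high attrition by 12 months without giving a figure.

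**The concern.** A rate ratio needs time in the denominator. Without an offset, a count model compares mean events per participant, and that equals a comparison of rates only when the arms have the same mean observed time. Here observed time will vary widely between participants, because events are mostly learned at assessments that many will miss.

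The at-least-once model has the same difficulty: someone observed briefly has had less chance of a recorded event.

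No interim analysis of harms is planned (SAP 3.6), so 6.10 is the planned inferential comparison of serious events between arms, with self-harm named as the main one expected. If retention differs between an app arm and usual practice, part of that difference would be reported as a difference in safety.

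**Working it through.** **The plan's own figure.** The only stated number that bears on this point is the attrition allowance. For PROMOTE, 2 × (1.960 + 1.282)² × (11.3/3.0)² = 298.2, so 299 per arm against 300 stated. Then 300/(1 − 0.40) = 500, as stated. The documents give no serious-event rate, no person-time and no dropout by arm. Those inputs below are assumptions.

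**Formula.** Let a share d of an arm be lost and observed for t months, with the rest observed for T months. Mean observed time is E = (1 − d)T + d·t. With a constant and equal true rate, the no-offset count ratio is E(A)/E(B), where A is the arm with more dropout.

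**Coverage by the 3-month recall item alone.** A participant who answers every assessment is covered for months 0–3 and 9–12, so T = 6. One who answers only at month 1 has t = 1.
- 45% against 30% lost: A = 0.55×6 + 0.45×1 = 3.75; B = 0.70×6 + 0.30×1 = 4.50; ratio 0.83. A true ratio of 1.2 would appear as 1.2 × 0.833 = 1.0.
- 45% against 35% lost: B = 0.65×6 + 0.35×1 = 4.25; ratio 3.75/4.25 = 0.88.

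**Full-year coverage for those retained (T = 12).**

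| Dropout, A vs B | t | E(A), E(B) | Count ratio |
|---|---|---|---|
| 40% vs 40% | 1 | 7.60, 7.60 | 1.00 |
| 45% vs 35% | 1 | 7.05, 8.15 | 0.87 |
| 45% vs 35% | 3 | 7.95, 8.85 | 0.90 |
| 50% vs 30% | 1 | 6.50, 8.70 | 0.75 |
| 50% vs 30% | 3 | 7.50, 9.30 | 0.81 |

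At 50% against 30%, a true ratio of 1.25 would appear as 1.25 × 0.747 = 0.93 (t = 1) or 1.25 × 0.806 = 1.01 (t = 3).

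**At least one event.** With yearly rate λ, p = (1 − d)(1 − e^(−λ)) + d(1 − e^(−λt/12)). For λ = 0.05, t = 1 and 50% against 30%, p is 0.0265 and 0.0354, an odds ratio of 0.74. Over λ = 0.02 to 0.10 and t = 1 or 3, the odds ratio runs from 0.735 to 0.805. At 45% against 35% it runs from 0.858 to 0.897.

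**Simulation.** There were 1,000 runs with 1,200 per arm (about 3599/3, both trials pooled), λ = 0.05, a true ratio of 1 and 50% against 30% dropout. Nominal 5% tests without an offset rejected in 23% (t = 1) or 17% (t = 3) of runs. With a log person-time offset they rejected in about 5%, with a mean ratio of 1.00. Restricting to completers also gave 1.00, because dropout was simulated as non-informative. The trials are analysed separately with fewer per arm, so the rejection rates there would be closer to 5%. The ratios do not depend on sample size.

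**The case against.** The strongest reply is that 6.10 is silent, not wrong. For efficacy, Protocol 10.3.2 says the analyses "will include participants with complete outcome data at 3-month follow-up". If observed data has the same meaning here, people lost before month 12 are excluded, exposure is common to everyone left, and the missing offset cancels when dropout is non-informative. A reader might infer that the logistic model codes a person lost at month 1 as event-free for the whole year. The intention-to-treat wording allows that, but the text does not state it. The completers-only reading has its own cost, since serious events reported by people who later left would drop out of the comparison.

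A reader might also infer that the arm with more dropout will look safer. That needs unequal dropout, and the documents give no figure by arm. Protocol section 8 argues that a shared format makes similar attrition more likely across the two active apps. Reminders and follow-up payments apply to every arm. Nothing comparable is argued for usual practice against the apps, so the possibility stays open without being shown.

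Nor is 6 months of coverage established. The AD-SUS can cover all 12 months for hospital and emergency events, and participants can report spontaneously. Missing one assessment is not permanent loss either, because SAP 5.4 keeps asking at later timepoints. In the other direction, telephone follow-up under Protocol 7.7 collects only the primary outcome measures, so a participant with outcome data may still lack adverse-event answers.

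Finally, decisions to discontinue the trial rest on cumulative committee review and not on these models, and non-completers are tabulated by arm in Tables A.12 and A.13. A retention difference would therefore be visible, though the models would not adjust for it.

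**Conclusion.** The gap is real: there is no exposure term, no definition of observed data for partial follow-up, and an incidence rate ratio with no person-time behind it. The direction and size of any bias are conditional. They require that partly followed participants are included and that dropout differs by arm. Under those conditions equal true rates would appear as about 0.83 to 0.88 (30% or 35% against 45% dropout; 6 against 1 months covered), or 0.75 to 0.90 under the 12-month scenarios. These are illustrations built on assumed dropout, coverage and a constant event rate, and they do not predict this trial's result. The documents do not support a flat statement that harm will be hidden. Neither reading of observed data is satisfactory as written: one lets exposure differ unadjusted, and the other discards reported events.

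**What to change.** In SAP 6.10:
- Define the safety set as all randomised participants with any adverse-event ascertainment.
- Define time at risk as randomisation to last ascertainment, restricted to the windows covered by the sources whose events are counted. Say how the AD-SUS and spontaneous reports enter. Merge overlapping windows, and leave out recall before randomisation.
- Keep numerator and denominator matched: an event outside every covered window is listed descriptively but not counted in the rate.
- Add log(time at risk) as an offset in the count model.
- For at least one serious event, replace or supplement the logistic model with an exposure-adjusted one, such as complementary log-log with the same offset.

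In Table A.14, report person-time by arm and the number in each arm with no ascertainment. The offset is undefined for that last group, so they must be shown separately.

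The cost is one derived exposure variable, which needs source-specific windows as well as visit dates, and some extra analysis. The offset does not correct informative dropout, such as leaving because of an event, and the report should say so.
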